12.1 Primary Objective

To measure the protective efficacy (personal protection) of repellent products, by comparison of the inhibition of *Musca sorbens* contacts on participants before and after their application.

The products will be some or all of the following insect repellents: DEET (N,N-diethyl-3-methylbenzamide), IR3535 (3-[N-butyl-N-acetyl]-aminopropionic acid ethyl ester), Picaridin (2-(2-hydroxyethyl)-1-piperidinecarboxylic acid 1-methylpropyl ester); PMD (para-Mentane-3,8-diol) or permethrin (m-Phenoxybenzyl)-cis,trans-3-(2,2-dichlorovinyl)-2,2-dimethylcyclopropanecarboxylate). Repellents will be applied 1) topically on the skin, or 2) in long-lasting, plastic formulations of that can be worn on the body (wearable repellent technologies). The insect repellent synergist Vanillin (4-Hydroxy-3-methoxybenzaldehyde) may be added to the long-lasting plastic formulations, to improve the duration of protection.

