14.2 Laboratory trial (London School of Hygiene & Tropical Medicine)

Laboratory studies will be conducted in specialised, Good Laboratory Practice (GLP)-accredited insect testing facilities at LSHTM. A colony of field-collected, but laboratory-reared, *Musca sorbens* are maintained by the lead investigator in insectary facilities at LSHTM, these will be used for all laboratory trials. We will enrol adults (>18 years) of both sexes, among staff and students of LSHTM, to this component of the trial.

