14.3 Field trial (Oromia, Ethiopia)

Field studies will be carried out in one woreda (district) in the West Arsi Zone of Oromia, Ethiopia, in the same approximate locality that the other Stronger-SAFE Phase II studies are being conducted, but in villages (kebeles) that have not previously been enrolled to any other Stronger-SAFE study component. Kebeles will be chosen where TF prevalence is believed to be low (TF1-9<40%). We will perform trachoma screening in the selected kebeles to confirm TF prevalence. We will select low prevalence areas as these studies do not incorporate clinical or Ct prevalence outcomes, requiring only fly populations, therefore we will aim to set the study site where there is minimal disease transmission but a high abundance of *Musca sorbens*. We will conduct a preliminary assessment of the suitability of study sites by visiting and observing the extent of local fly-eye nuisance among children. We will enrol households with children aged three to 12 years, as they are at increased risk of TF relative to adults, and also tend to experience higher levels of face fly nuisance. This field study location will provide an excellent context for informing on the wider applicability of the study results, due to both the very high TF prevalence rates (21) and fly population densities (29) experienced in this area. Small-scale field repellency trials will be conducted at the participant's houses.

15 Trial eligibility and withdrawal criteria

Participants will be healthy individuals, and will be included in the study if they meet all of the following criteria:

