15.1 Laboratory trial eligibility criteria

1. Participant is aged 18 years and ≤ 65 years and in good health
2. Participant has a good understanding of the procedures of the study and agrees to abide to these procedures
3. Participant is able to communicate well with the investigator, and attend the laboratory for all aspects of the laboratory studies
4. Participant has no known adverse reactions, or evidence at screening of adverse reactions, to the commercially available repellents DEET, PMD, IR3535, Picaridin or Permethrin, or to Vanilla
5. Participant has no known history of skin allergies or hypersensitivity to topical creams
6. Participant agrees to a pre-trial skin reactivity test for all the repellents that will be used in the trial
7. If in the event of the participant experiencing an adverse reaction to a repellent during the trial, the participant agrees to inform his/her general practitioner and seek appropriate treatment if necessary
8. Participant is willing to allow laboratory-reared *Musca sorbens* flies to land and crawl on their arm, during the modified arm-in-cage assay, for periods of up to ten minutes at a time
9. Participant agrees not to use any perfumed or scented product, including bathing products, for a 24-hour period before each laboratory session
10. Participant has signed informed consent
11. Participant is not a smoker, and will agree to refraining from smoking for the 12 hours before each laboratory trial

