20.1 Laboratory trials

Participants will be recruited through standard recruitment methods, including emails, posters, leaflets and other advertising routes to staff and students of LSHTM and other members of the public. Participants will be fully informed before the study and it will be made clear that they can withdraw from the study at any time. Participants will be given and asked to read the Participant Information Sheet (Appendix 1) and Product Information Sheet (Appendix 2) which describes the tests which they will take part in, and a consent form (Appendix 3) which must be signed before the test begins. Because in the laboratory trials all participants will test all products and all concentrations, this study is non-randomised.

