
PRIMARY EYE IRRITATION
 
Category I Corrosive (irreversible destruction of ocular tissue) or corneal involvement or irritation persisting for more than 21 days.
 
DANGER No symbol Corrosive. Causes irreversible eye damage.
 
Category II Corneal involvement or irritation clearing in 8-21 days.
 
WARNING No symbol Causes substantial but temporary eye injury.
 
Category III Corneal involvement or irritation clearing in 7 days or less.
 
CAUTION No symbol Causes moderate eye irritation.
 
Category IV Minimal effects clearing in less than 24 hours.
 
No signal word, symbol or hazard statement required. Registrant may choose to use Category III statement.
	
SERIOUS EYE DAMAGE/EYE IRRITATION
 
Category 1 Effects on the cornea, iris or conjunctiva that are not expected to reverse or that have not fully reversed within 21 days.
 
DANGER Corrosion symbol in diamond. Causes severe eye damage.
 
Category 2A Effects on the cornea, iris or conjunctiva that fully reverse within 21 days.
 
WARNING Exclamation mark in diamond. Causes severe eye irritation.
 
Category 2B Effects on the cornea, iris or conjunctiva that fully reverse within 7 days.
 
WARNING No symbol Causes eye irritation.

Figure 9. A comparison of chemical hazard classification and labeling: Office of Pesticide Programs (OPP) and the Globally Harmonized System of Classification and Labelling of Chemicals (GHS) (63). DEET was found to be in GHS category 2 (level unspecified) (61).

DEET has caused adverse reproductive and fetal effects in animals, and may cause central nervous system effects. There are no known carcinogenic chemicals in this product. The safety of daily application of (DEET) in the second and third trimesters of pregnancy was assessed as part of a double-blind, randomized, therapeutic trial of insect repellents for the prevention of malaria in pregnancy. The results of the study suggest that the risk of DEET accumulating in the fetus is low and that DEET is safe to use in later pregnancy (64).

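### The laboratory eligibility criteria are silent on pregnancy, although the plan itself reports fetal effects of DEET in animals and offers human reassurance only for later pregnancy

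*Combined protocol and SAP*

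**What the plan says.** **Hazard.** Section 22.2.1 states that "DEET has caused adverse reproductive and fetal effects in animals, and may cause central nervous system effects". It then cites one human trial, of daily use in the second and third trimesters, and takes from it that "DEET is safe to use in later pregnancy". It says nothing about the first trimester.

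**Who may enter.** Section 15 opens by saying that healthy individuals "will be included in the study if they meet all of the following criteria". For the laboratory trial, the first of 11 criteria in 15.1 is "Participant is aged 18 years and ≤ 65 years and in good health". Section 14.2 says "We will enrol adults (>18 years) of both sexes, among staff and students of LSHTM", section 20.1 extends recruitment to the public, and section 19.1 prefers equal numbers of men and women.

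**Who is exposed.** DEET is a candidate and not a certainty: section 12.1 says "The products will be some or all of the following insect repellents". Once products are chosen, exposure is shared by all: "Because in the laboratory trials all participants will test all products and all concentrations, this study is non-randomised" (section 20.1). Exposure begins before the first test session, because 15.1 also requires that "Participant agrees to a pre-trial skin reactivity test for all the repellents that will be used in the trial".

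**The concern.** The plan names a reproductive hazard for one candidate product but draws no consequence from it for enrolment. Elsewhere a stated hazard does change the design. PMD is kept out of topical use because of advice about children's faces (sections 16.1.2 and 22.2.4), and vanillin is confined to wearable devices because of eye irritation (section 22.2.6). For DEET and pregnancy, the supplied text contains no criterion, no question and no reasoning for leaving pregnancy open.

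What is at stake is participant safety, not the validity of an estimate. Section 22.5 says laboratory volunteers gain nothing from taking part, so a risk that one line of text could avoid is hard to justify. Status can also change after screening: visits are repeated, and wearable devices are followed for a month (sections 15.4 and 21.1.4).

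**Working it through.** The plan states no figure on this point, so the check is mainly a reading of every place where a pregnancy condition could sit.

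1. **Summary laboratory criteria (section 5).** Both sexes, full health, no adverse reactions to the products, willingness to undergo the cage assay. Pregnancy is not mentioned.
2. **Section 15.1.** Eleven criteria on age and health, understanding, availability, adverse reactions, skin allergy, the skin test, informing the GP, fly contact, scented products, consent and smoking. Pregnancy is not mentioned, and good health does not exclude a healthy pregnant woman.
3. **Entry rules elsewhere.** The list in 15.1 is not complete. Section 25 adds a 48-hour ban on repellents. Section 28.1 adds a 72-hour wait after the skin test and a bar on known allergy to ingredients. None concerns pregnancy.
4. **Data collected (section 26.1.1).** The person variables are body weight and tympanic temperature. The item for eligibility details is not broken down.
5. **Removal (section 15.3).** The Chief Investigator may remove a participant for safety, or if a condition develops that could interfere with participation. Either ground acts after entry and needs the pregnancy to be known; no supplied step asks.
6. **Safety follow-up (sections 28.1 to 28.3).** Participants are monitored in sessions and contacted within 72 hours of testing. Later monitoring is passive, and ongoing events are followed for at most 30 days. A congenital anomaly counts as a serious event, reportable to the Chief Investigator within 24 hours. No step asks for the outcome of a pregnancy, which may come months after the 30 days have passed.

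Together: the entry rule admits anyone healthy who meets the list; the list is silent on pregnancy; every participant receives every selected product. If DEET is among them, a woman known to be in her first trimester is eligible and would be exposed.

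**Amount applied.** Inputs: 1.4 ml per forearm and a 20 % ceiling (section 16.2.1); 20 % is taken as 200 mg/ml, which is an assumption. To test it against the plan's own cheek figure in 22.2.1:

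- Area of two 6 cm circles: 2 × 28.27 = 56.5 cm².
- Volume at 1 ml per 600 cm²: 56.5 / 600 = 0.0942 ml.
- Amount: 0.0942 × 200 = 18.85 mg, which matches the stated 18.85 mg.

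The same conversion for the forearm gives 1.4 × 200 = **280 mg** for one application at the ceiling. In stage one (section 21.1.3.1) up to five increasing doses are applied in series in one session, so 280 mg is one application and not the session total.

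**The case against.** The strongest reply is that the documents most likely to deal with pregnancy are not available. These are the participant information sheet, product information sheet and consent form (Appendices 1 to 3), the DEET safety data sheet (Appendix 10) and the screening form (Appendix 17). A reader might infer that pregnant women will be unscreened or uninformed. The supplied text does not support that; it shows only that the criteria themselves are silent. This part of the reply stands. However, a question on the form would still not place a criterion in 15.1.

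Second, the hazard statement is thin: one sentence, with no species, dose or route. A reader might infer that the laboratory applications carry a demonstrated fetal risk, or might compare 280 mg with the acceptable exposure level in 22.2.1. Neither step is sound. The section does not show risk at these exposures, its human evidence is reassuring as far as it goes, and the acceptable exposure level is not a pregnancy limit.

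Third, there are general protections: discretionary removal, washing after testing, ethics review and an independent data monitoring committee. They are real, but none asks about pregnancy or obtains its outcome.

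Fourth, self-declaration fits the gap imperfectly. It misses early pregnancy that is not yet recognised, and it excludes later pregnancy, for which the cited evidence is favourable. That is fair, and it limits what the fix can achieve. It is not a reason to leave known first-trimester exposure unaddressed.

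**Conclusion.** The point holds as an omission in the stated criteria. Under the supplied text, a woman known to be pregnant, including in the first trimester, may enter the laboratory trial and receive DEET if it is selected, while 22.2.1 gives human reassurance for later pregnancy only.

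The scale is small. It concerns at most the women among 17 volunteers, and the number who are pregnant may be zero. The conclusion is conditional on DEET being selected and on the unseen appendices not already covering the matter, so confidence is medium. It does not extend to the field trial, whose participants are aged 3 to 12. Nor does it extend on the same ground to the other five actives, for which section 22.2 reports no fetal hazard and cites no pregnancy evidence.

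This is a cheap safety improvement that the sponsor should make. It does not affect any endpoint or analysis.

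**What to change.** - **Section 15.1:** add *Participant is not known to be pregnant*, by self-declaration at screening and before the skin reactivity test. Instruct participants to report a pregnancy that becomes known before any later session, and to stop testing. Repeating the question at every session is not needed.
- **Screening form (Appendix 17):** align it if it does not already ask.
- **Section 28.1, laboratory trial only:** state that any pregnancy that becomes known during participation is recorded and its outcome requested from the participant.
- **If DEET is not selected:** the sponsor may decide whether to keep the line.

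The cost is one criterion, one screening question with a reporting instruction, and one sentence on follow-up. A few volunteers may be ineligible or have to stop, and the limit of self-declaration remains.

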22.2.2 IR3535

Insect repellent IR3535 is a liquid containing 98 % active ingredient 3-[N-butyI-N-acetyl]-aminopropionic acid ethyl ester, and 2 % inert ingredients (65). This insect repellent is structurally similar to naturally occurring beta-alanine, and is itself a substituted beta amino acid. It has been used to repel mosquitoes, deer ticks, lice and biting flies (65). At initial assessment, IR3535 was found to have low acute toxicity, and with no reports of adverse health effects on humans. However, IR3535 has been found to cause conjunctival irritation at concentrations of 10, 15 and 20 % in rabbits, further, some corneal opacities were observed which recovered in 8-21 days (66). At this time (2001) the LD₅₀ given was >14,000 mg/kg orally and >10mg/kg dermally (66). In 2014 the US EPA initiated review of IR3535. They found that all human health assessment data requirements had been addressed, and between 1991 and 2014 they found 211 reports of adverse incidents in humans, which included reports of running nose and eyes and eye irritation (67). Following the review, subsequent fact sheets and technical documents state that there is reliable data regarding IR3535 to support the conclusion that this insect repellent is practically non-toxic to mammals, including infants and children (65). They found no threshold effect and therefore did not publish a margin of safe exposure. However, it was noted that eye irritation can occur if IR3535 enters the eyes (68).

Current European Union guidelines concerning the risk to consumers for the use of IR3535 sets the AOEL_{short term} (Acceptable operator exposure level for short term use) at 6 mg/kg bw/day (69). For an estimation of the percentage of this AOEL that will be topically applied of active ingredient, for a hypothetical dose range of maximum 20 % and a range of hypothetical children's body weights, see Appendix 9, for the material safety data sheet (MSDS) see Appendix 11.

22.2.3 Picaridin

Picaridin, also known as icaridin, is a synthetic compound designed to resemble the natural compound piperine, which is found in the group of plants that are used to produce black pepper (70). It was first reviewed for toxicity by the WHO in 2001, and found to have a good safety profile with negligible dermal and limited ocular irritation capacity in rabbits (this was based on a summary of toxicity studies provided by Bayer AG, Germany) (66). The recommended target dose was 0.3 mg active ingredient/cm² of skin. In 2004 the WHO published the results of OECD test number 405 (Acute eye irritation/corrosion) and found Icaridin to be a slight irritant. In 2014, the US EPA reviewed the use of Picaridin, to determine whether it met the federal insecticide, fungicide and rodenticide act (FIFRA). At that time, Picaridin was second only to DEET in use in the US (71). Previously reported oral and dermal toxicological effects were determined to be species-

specific (conducted in rodents) and not relevant to humans. In a review of human incidents, 214 minor incidents were reported between 2009 and 2014, which usually involved skin, eye or respiratory irritation. Importantly, the incidents were all of minor severity and resolved rapidly. In another database (Centers for Disease Control and Prevention/National Institute for Occupational Safety and Health (CDC/NIOSH)), 22 cases were reported between 1998 and 2010. Most cases (18 of the 19 involving picaridin alone) were low in severity, largely involving dermal or eye irritation, however, in one case where picaridin was directly applied to the face of an infant, the case was moderate in severity. The US EPA identified no human health risks associated with the use of Picaridin. Most recently, Picaridin has been classified by the US EPA as being of low acute oral, dermal and inhalation toxicity, and Toxicity Category III for primary eye and skin irritation (Category III = slightly toxic. Toxicity category not specified but assumed to be OPP, Figure 9) (72). The toxicology database is considered complete and no additional studies are required. The US EPA stated that they believe that the normal use of Picaridin does not present a health concern to the general U.S. population (72). The acute dermal LD₅₀ given was >2000 mg/kg (Limit test).

Current European Union guidelines concerning the risk to consumers for the use of Icaridin sets the AEL_{short term} (Acceptable exposure level for short term use) at 3.1 mg/kg bw/day (73). For an estimation of the percentage of this AEL that will be topically applied of active ingredient, for a hypothetical dose range of maximum 20 % and a range of hypothetical children's body weights, see Appendix 9, for the material safety data sheet (MSDS) see Appendix 12.

22.2.4 PMD

PMD, structurally similar to menthol, can be derived from the essential oil of the leaves of *Corymbia citriodora*, or from the synthetic citronellal. When *C. citriodora* oil is refined to increase the PMD content, it is known as Oil of Lemon Eucalyptus (OLE). PMD has been on the market as an insect repellent since 1998 (74), and is considered to be an eye irritant (Toxicity Category 1), and this is the only adverse effect that has been found in studies using lab animals (57). These adverse effects have led to precautions around the use of PMD, crucially, it is advised against the use of PMD on the face or hands of children (57). For this reason, PMD will not be assessed for use as a topical repellent in this clinical trial. However, the use of PMD in a wearable repellent device would be permitted, as (1) the device would not be worn on the face, and (2) exposure from a wearable repellent device is much lower as there is not direct dermal application.

Other than eye irritation, PMD is not expected to pose any health risks to people, including children (57), and no AEL/AOEL are stated. Further, due to the avoidance of PMD as a topical repellent, such values would not be relevant here. For the material safety data sheet (MSDS) see Appendix 13.

22.2.5 Permethrin

Permethrin, a member of the pyrethroid class of insecticides (75), is classed as a repellent when used to pre-treat clothing, and is the only insect repellent that is currently used for factory treatment of clothing (76). As with PMD, in this study Permethrin will only be considered for use in the wearable repellent devices.

In 2009, the US EPA evaluated multiple scenarios for permethrin factory-treated clothing, including toddlers wearing or mouthing the clothing, and found the product unlikely to pose any

significant immediate or long-term hazard to those wearing the clothing (76). Multiple studies have demonstrated that maximum permethrin uptake from impregnated clothing is five times lower than the regulations established by the WHO and US EPA, and therefore have concluded that health impairments are unlikely (77–79). This study will focus on the use of polymer coated fabric, which has the lowest skin absorption rate when compared to other types of treated clothing (39). The majority of studies also show that impregnated clothing is usually comfortable, non-irritating and non-odorous (37).

When used at appropriate concentrations, insecticide-treated clothing is deemed safe. For example, one study showed that permethrin is transferred from clothing to skin at a rate of 0.49 % per day from fabric treated with permethrin at a rate of 0.125 mg/cm². This equated to 0.00006 mg/kg bw/day, with the permethrin AEL_{medium term} (Acceptable exposure level for medium term use) 0.05 mg/kg bw/day (80). For the material safety data sheet (MSDS) see Appendix 14.

In summary, the amount of permethrin that is allowed in treated fabric is low, and from the fabric it is thought to be poorly absorbed through the skin.

The following international agencies recommend insecticide treated apparel:

- The U.S. Centre for Disease Control and Prevention (CDC)
- The World Health Organization (WHO)
- National Institute for Occupational Health and Safety
- The American Academy of Family Physicians
- The Public Health Agency of Canada

22.2.6 Vanillin

Vanillin is derived from extract of the vanilla bean. Some studies have indicated that this compound can increase the protection time of insect repellents (81). Because vanillin is considered to cause serious eye irritation, the use of vanillin in this trial would be restricted to use in the wearable repellent technologies, which would not be proximate to the eye. For the MSDS see Appendix 15.

22.2.7 Specific risk from application of topical repellents to the face (field trial only)

Due to the nature of the eye-seeking vector in question, it is unavoidable that topical repellents must be applied to the face. As per section 16.1, the repellent active ingredients that will be tested topically (DEET, IR3535 and Picaridin) have been chosen because they do not carry a specific risk of eye irritation beyond what would reasonably be expected through application of a chemical product.

It should be noted that commercially available repellent products do have instructions on the label that recommend application to the face. However, care must be taken when doing so. In the field trial, topical repellents will be applied in a 6 cm diameter circle on the cheek, at least 3 cm (measured by three finger-breadths) below the eye and positioned away from the nose and mouth. The repellents will be administered by Stronger-SAFE ophthalmic nurses, who will be present at all times during field testing, see section 28 for more information regarding participant

care during adverse events. The importance of preventing inadvertent transfer of topical repellent from the face to the eye will be fully communicated to participants and their caregivers.

